## 3.2 Primary Study Endpoints

The primary endpoint of this study will be to determine if the rate of void trial failure after TLH is different after the autofill method versus the backfill method.

## 3.3 Secondary Study Endpoints

The following study endpoints will also be compared between participants undergoing backfill void trial and autofill void trial:

- The time to discharge will be measured for each participant. This will be determined by calculating the time between arrival to the PACU and the time of discharge using documentation from Epic and from the case report forms (CRFs).
- After discharge, participants will be monitored for any encounters for urinary retention (in our hospital system) and will be asked at their 10-14 day post-operative visit if they had a Foley catheter placed outside the hospital. Additionally, any participant who fails their 2nd void trial will be noted. The incidence of urinary retention post-discharge will be determined using this data.
- Any participant diagnosed with a culture-proven UTI will be noted.
- The IIQ-7 will be used to determine if there are any changes to the participants' short term quality of life before and after surgery.
- The PPBC will be used to determine if there are any changes to the participants' perception of bladder function before and after surgery.

- Participant satisfaction level with the method of void trial will be collected at the 10-14 day post-operative visit and compared between the two methods of void trial.

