## 2.2 Secondary Objectives

The following variables will also be compared between participants undergoing backfill void trial and autofill void trial:

- Time to discharge: time from arrival to post-anesthesia care unit (PACU) to time of discharge
- Incidence of urinary retention after discharge from hospital
- Incidence of UTI in the first 2 weeks after surgery
- Participants' short term quality of life during the first 2 weeks after surgery
- Participants' satisfaction with the void trials

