## 6.6 Post-op Week 2 Visit

At the post-operative visit 10-14 days after the surgery, the participants will be evaluated and examined in the office. They will be asked to complete a questionnaire which includes the IIQ-7, the PPBC, and a void trial satisfaction question (see attached "post-operative participant questionnaire"). Participants will also be asked if they obtained a Foley catheter outside of the hospital at any urgent care centers, other doctors' offices, or emergency rooms. Additionally, participants will be asked if they have any urinary problems including dysuria, hematuria, frequency, hesitancy, urgency, or incomplete emptying. If any urinary complaints exist, participants will be asked to provide a urine sample for testing by urinalysis and urine culture. Participants will be treated per physician preference. After treatment, participation in the study will be considered completed.

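### Post-discharge retention is counted from any encounter inside the hospital system but only from a reported Foley outside it, so some retention treated elsewhere is missed

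*Combined protocol and SAP*

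**What the plan says.** The objective in 2.2 is broad: "Incidence of urinary retention after discharge from hospital". Nothing there ties it to a device.

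Section 3.3 turns it into an endpoint with three sources.

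- **Inside the system:** encounters ("participants will be monitored for any encounters for urinary retention (in our hospital system").
- **Outside the system:** participants "will be asked at their 10-14 day post-operative visit if they had a Foley catheter placed outside the hospital".
- **Second void trial:** any participant failing the second "void trial will be noted. The incidence of urinary retention post-discharge will be determined using this data". This sentence also closes the list of sources.

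Section 6.6 repeats the outside question in the same terms: "Participants will also be asked if they obtained a Foley catheter outside of the hospital at any urgent care centers". It goes on to name other practices and emergency departments. Section 3.1 has the same question.

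At that visit, "participants will be asked if they have any urinary problems including dysuria, hematuria, frequency, hesitancy, urgency, or incomplete emptying". The step specified for a positive answer is laboratory work: "If any urinary complaints exist, participants will be asked to provide a urine sample for testing by urinalysis and urine culture". The calendar in 6.7 shows no post-void residual at week 2.

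**The concern.** Inside the system the criterion is the condition; outside it is one particular device. The same clinical event is counted or not according to where the woman went. An in-system visit for retention counts whether or not a catheter was left in. An outside visit settled by a single in-and-out catheterisation, or with no catheter, does not.

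Such management is foreseeable from the protocol itself. Section 3.1 mentions straight catheterisation and self-catheterisation, and its void-trial failure rule rests on inability to void or the residual volume.

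Post-discharge retention is the natural check on a day-0 method that passes more women. The third source reaches only women who failed on day 0, because only they have a second trial (6.4). Women who passed are found only through the other two sources, one of which is narrower than the objective.

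**Working it through.** **Reading the text.** Four cases, set against the rule in 3.3:

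| Event after discharge | Counted under 3.3? |
|---|---|
| In-system encounter for retention, with or without a Foley | Yes |
| Outside care with a Foley placed, reported at the visit | Yes |
| Outside care by in-and-out catheterisation, or no catheter | No |
| Retention diagnosed at the 10-14 day visit | Not stated; can be read as an in-system encounter |

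Sections 3.4 (complications) and 8.2 (adverse-event questioning) could bring the third case into the data. Neither is named as a source for this endpoint.

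**Size.** The plan gives no rate, power or sample size for this endpoint, so there is no figure of its own to reproduce. From 7.1 I take 38 women per arm and the planning failure rates of 4.9% (autofill) and 28.3% (backfill). Recomputing that sample size gives 39 per arm, either one-sided with continuity correction or two-sided without. That is close enough for this purpose.

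Women passing on day 0:

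- autofill: 38 × (1 − 0.049) = 36.1
- backfill: 38 × (1 − 0.283) = 27.2

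The next three inputs are **assumptions**; the documents give none of them: 5% retention after a pass; half of it seen outside; 0-50% of that managed without a Foley.

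- Share of these events lost: 0.5 × (0 to 0.5) = 0 to 25%
- Events, autofill: 36.14 × 0.05 = 1.807; lost: 0 to 0.452
- Events, backfill: 27.25 × 0.05 = 1.362; lost: 0 to 0.341

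The loss is proportional to the 5%: at 10% the autofill maximum would be 2 × 0.452 = 0.90.

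**Effect on the comparison.** With the same proportional loss in both arms:

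- ratio of events after a pass, full capture: 1.807 / 1.362 = 1.33
- ratio at 25% loss: (1.807 − 0.452) / (1.362 − 0.341) = 1.355 / 1.021 = 1.33
- shift in the difference between arms: 0.452 − 0.341 = 0.111 woman, or 0.111 / 38 = 0.3 percentage points

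**Power, for context.** With 38 per arm, two-sided 0.05, and assumed true rates of 15% and 5%, power is about 30% with full capture and 23% with 75% capture. It is low either way.

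**The case against.** The strongest reply is that the gap is slight and partly covered. On the assumptions above it costs less than half an event per arm, the range includes no loss at all, and the endpoint is secondary and unpowered. Sections 3.4 and 8.2 may well record the missing cases. The questionnaire and case report form are attachments (14.0) not available here, and their wording may be broader than the summary in the protocol. A Foley is also concrete and easily recalled, so the narrow question has some merit for specificity.

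Most of that stands as a limit on size. It does not remove the mismatch: 3.3 lists its sources and says incidence comes from them. Adding adverse-event reports later would be an unplanned choice by staff who know the allocation (5.8).

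A reader might infer three stronger things that the documents do not support.

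- **That retention present at the 10-14 day visit is lost altogether.** That visit is an examination in the trial's own clinic, with treatment left to the physician, so retention diagnosed there can be read as an in-system encounter. What is missing is a sentence saying so.
- **That hesitancy or a sense of incomplete emptying at the visit is uncounted retention.** These are symptoms, not the event.
- **That the gap favours one method.** The planning rates in 7.1 have autofill passing more women, while the hypothesis in 1.5 expects fewer failures with backfill. Equal proportional loss also leaves the ratio of events after a pass unchanged.

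**Conclusion.** The mismatch is real. As written, 3.3 classifies the same event differently by site of care and falls short of the objective in 2.2. The consequence is a modest under-count of one secondary endpoint: 0 to 0.45 events in autofill and 0 to 0.34 in backfill at the planning rates, resting on the three assumed inputs. It falls mainly on women who passed the day-0 trial, and so more on whichever arm passes more of them; which arm that will be is open. With only one or two such events expected per arm, a single misclassified woman is visible in the result, so the rule is worth aligning. The primary endpoint and its sample size are not touched.

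**What to change.** 1. In 3.1, 3.3 and 6.6, and in the questionnaire or case report form if they use the same wording, replace the Foley-only question with one such as: *Since leaving hospital, were you seen anywhere outside our hospital system for urinary retention (being unable to pass urine), or did you have any catheter placed for it, indwelling or in-and-out?*
2. In 3.3, state that outside events count by the same rule as in-system encounters, confirmed from outside records where these can be obtained.
3. In 3.3, state that retention diagnosed at the 10-14 day visit counts as an in-system encounter.

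Keeping the question to retention, not to urinary symptoms in general, prevents the outside rule from becoming looser than the inside one. No extra residual measurement is needed.

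The cost is one reworded question, two sentences in 3.3 and occasional requests for records. The downside is small: some outside events will rest on self-report from participants who know their method, as the present Foley question already does.

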## 3.4 Primary Safety Endpoints

All intra-operative and post-operative complications will be recorded for each participant. If any adverse events are related directly to the void trial methods, these will be documented and reported to the IRB and the study will be stopped immediately for that particular participant.

#### 4.0 SUBJECT SELECTION AND WITHDRAWAL

#### 4.1 Inclusion Criteria

Subjects must meet the following inclusion criteria to be eligible for the study:

- 1. Females at least 18 years of age
- 2. Understand and voluntarily sign an informed consent form
- 3. English-speaking (able to read and understand English)
- 4. Undergoing robotic or laparoscopic TLH for benign indication

### 4.3 Subject Recruitment and Screening

Patients will be recruited from the Cleveland Clinic Florida Department of Gynecology, primarily from two providers' patients—[name] and [name]. These physicians will see and book patients for TLH as normally in the office. All patients scheduled for TLH will be offered enrollment in the study per the aforementioned inclusion and exclusion criteria. Enrollment will occur at the pre-operative consultation or by telephone prior to day or surgery. A brief description will be provided including the risks/benefits of enrolling in the study. An opportunity for questions will be provided. Patients who do not wish to participate in the study will not be enrolled. On the day of the surgery, in a private area of the pre-operative suite, a member of the research team will discuss the study with the patient to readdress the protocol and answer any new questions. An approved informed consent document will be signed at the pre-operative consultation if the patient is agreeable to participation. If the patient is enrolled by telephone, the informed consent document will be signed the morning of surgery.

#### 4.4 Early Withdrawal of Subjects

Patients may withdraw from the trial at any time and for any reason. Some reasons for early withdrawal also exist. One such reason is malignancy in the final pathology report, conversion

to laparotomy, or intraoperative bladder injury requiring Foley catheter for a prolonged period of time. Early withdrawal will occur if a patient's procedure becomes more than the scheduled case only; for example, if the bowel is injured and the need to perform a bowel resection arises then the patient will be withdrawn from the study. Withdrawal from this study will not affect access to standard clinical care for post-operative visits or other gynecologic needs.

## 4.5 Data Collection and Follow Up for Withdrawn Subjects

If patients withdraw prior to the research intervention (backfill versus autofill void trial), they will be completely removed from the study and not followed according to the research protocol. Post-operatively, the patient's surgeon will choose the void trial method per his preference. Patients will receive routine post-operative care by their provider. If withdrawal occurs by patient preference or by meeting one of the early withdrawal criteria, the patient will be asked to follow-up according to standard of care at the 10-14 day post-operative visit. The reason for her withdrawal will be recorded. However, no further data will be collected about that patient for research purposes. If any complications arise, she will be treated appropriately.

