## 8.2 Recording of Adverse Events

At each contact with the subject, the investigator will seek information on adverse events by specific questioning and, as appropriate, by examination. Information on all adverse events will be recorded immediately in the source document, and also in the appropriate adverse event section of the case report form (CRF). All clearly related signs, symptoms, and abnormal diagnostic procedures results will also be recorded in the source document. The clinical course of each event will be followed until resolution, stabilization, or until it has been determined that the study treatment or participation is not

the cause. Serious adverse events that are still ongoing at the end of the study period will be followed up to determine the final outcome. Any serious adverse event that occurs after the study period and is considered to be possibly related to the study treatment or study participation will be recorded and reported immediately.

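### Section 4.5 ends research data collection for women withdrawn after their void trial, so two-week outcomes and later non-serious complications are lost for patients whom 7.3 counts as treated

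*Combined protocol and SAP*

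**What the plan says.** Section 4.5 first deals with women who leave before the void trial; they are removed from the study altogether. It then turns to a second situation: "If withdrawal occurs by patient preference or by meeting one of the early withdrawal criteria". Such a woman still has a clinic appointment, since "the patient will be asked to follow-up according to standard of care at the 10-14 day post-operative visit", and her reason for leaving is noted. The section closes with "However, no further data will be collected about that patient for research purposes. If any complications arise, she will be treated appropriately". Nothing limits this second rule to women who have not yet been treated.

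Section 4.4 lets a woman withdraw at any point. Its investigator-led reasons are conversion to laparotomy, bladder injury, a procedure that grows beyond the one scheduled, and a pathology finding: "One such reason is malignancy in the final pathology report".

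Four other sections bear on the same women:

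- Section 3.4: "All intra-operative and post-operative complications will be recorded for each participant". For adverse events directly related to the void trial method, "these will be documented and reported to the IRB and the study will be stopped immediately for that particular participant".
- Section 8.2: "The clinical course of each event will be followed until resolution, stabilization", or until study treatment or participation is ruled out as the cause. It makes no exception for women who have left.
- Section 7.3 analyses every treated woman and excludes only those who leave before the intervention.
- Section 3.3 lists the outcomes that depend on follow-up: post-discharge retention, culture-proven UTI, IIQ-7, PPBC and satisfaction.

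**The concern.** The intervention is a single episode on the day of surgery. Once the first void trial is over, the research still to be done is mainly follow-up: any repeat void trials, the 10-14 day outcomes and adverse event recording. A rule that ends data collection at that stage does not undo the woman's exposure to the assigned method. It only leaves gaps in the secondary and safety comparisons.

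Those gaps fall on women whom 7.3 retains, and the statistical methods in 7.2 do not say how missing two-week data are handled. Staff also receive incompatible instructions. For a non-serious complication arising after withdrawal, they cannot both follow 4.5 and satisfy 3.4 and 8.2. The interim safety look in 8.5 uses adverse event counts, so the wording matters there too.

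**Working it through.** **1. Does the rule reach treated women?** Yes, by two routes.
- Patient preference: 4.4 sets no time limit.
- Final pathology: the report follows surgery and would normally arrive after the void trial in the PACU. The documents do not date it, so this timing is an inference.

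The other 4.4 reasons arise during the operation and normally precede the void trial. They add little here.

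**2. What is lost and what is kept?**
- Kept: the first void trial result, which is fixed on day 0. Section 7.3 implies that data already collected on treated women are used.
- Lost: whatever remains of post-discharge retention, UTI, IIQ-7, PPBC and satisfaction.
- At risk: later complications. Serious events have extra cover, because 8.3.2 sends all of them to the IRB and 8.2 captures possibly related ones even after the study period. Non-serious later events have no such cover.

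**3. The instructions for a treated woman who is then withdrawn**

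| Section | Instruction |
|---|---|
| 4.5 | "However, no further data will be collected about that patient for research purposes" |
| 3.4 | Record all complications, for each participant |
| 8.2 | Follow each event to an end point, with no exception |
| 7.3 | Include her in the analysis |

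The first row cannot be carried out together with the second and third. It also leaves the fourth with missing values.

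**4. The woman stopped under 3.4.** Section 3.4 says the study is stopped for her. It does not call this a withdrawal, and 4.4 does not list a void-trial adverse event. Whether 4.5 applies to her is therefore unstated. Her triggering event must be documented and reported under 3.4 and followed under 8.2.

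**5. Size.** Section 7.1 gives 76 women plus 10%: 76 × 1.10 = 83.6, rounded up to the stated 84. The allowance for dropout is 84 − 76 = 8. The documents give no rate of withdrawal after the void trial, so the number lost (k) is an assumption. Share of two-week data lost = k / 84:

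- k = 1: 1/84 = 1.2%
- k = 2: 2/84 = 2.4%
- k = 4: 4/84 = 4.8%
- k = 8 (the whole allowance): 8/84 = 9.5%

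As an illustration of sensitivity, take an arm of 84/2 = 42 with an assumed 4 two-week events, a rate of 4/42 = 9.5%. If one woman with an event is no longer followed, the observed rate is 3/41 = 7.3%. If two are not followed, it is 2/40 = 5.0%. This shows only how few events are involved; it does not estimate bias.

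**The case against.** A reader might infer that a woman harmed by her void trial disappears from the data at that moment, so that the more harmful method looks safer. The documents do not support this. It requires reading the stop in 3.4 as a withdrawal under 4.5, which no section says. Even on that reading, the triggering event is documented, reported to the IRB and followed, and 8.6 puts the number and type of adverse events on the case report forms. Only a later event could be missed.

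Further points stand against a strong reading:

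- The primary endpoint is settled on day 0.
- Pathology withdrawals should not depend on the assigned method, so that loss should not favour an arm. If the report arrives after the 10-14 day visit, the two-week data are already in hand.
- Excluding malignancy fits the benign-indication population in 4.1 and 4.2.
- A large-sounding UTI figure is easy to produce. At the 4% and 6% rates cited in 1.3, an arm of 42 expects 42 × 0.04 = 1.7 or 42 × 0.06 = 2.5 cases, so one lost case is 40-60% of them. At that study's 18% rate, 42 × 0.18 = 7.6 and one case is about 13%. These are properties of small counts, taken from a study of a different hysterectomy technique.
- The consent form and case report form are attachments not available here and may address data use after withdrawal.

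All of this limits the point to secondary and safety data. It does not remove the explicit instruction in 4.5 or its conflict with 3.4 and 8.2.

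**Conclusion.** The point holds as a stated rule that discards follow-up on treated women and contradicts the protocol's own safety sections. It also holds as a gap: 3.4 does not say whether a woman stopped after a void-trial-related event is still followed. It does not establish bias between arms or any effect on the primary comparison, provided data already collected are retained.

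The amount lost cannot be known from the documents. The 1.2% to 9.5% range rests on an assumed 1 to 8 women out of all 84, and it is an upper figure for any woman who leaves after some of her outcomes have been recorded. Whether the clinical rule for stopping a participant is right is not judged here.

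**What to change.** Amend 3.4 and 4.5 to distinguish stopping study procedures from ending data collection. For any woman who has started her void trial:

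1. Keep the data already collected.
2. Continue to record complications and follow adverse events under 8.2.
3. Collect the retention, UTI, IIQ-7, PPBC and satisfaction outcomes at the 10-14 day visit.
4. End collection only if she herself withdraws permission for data collection.

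State in 3.4 that this applies to a woman for whom the study is stopped after a void-trial-related event. Do not use malignancy on final pathology as a reason to end data collection. Reconcile 4.5 with 3.4, 7.3 and 8.2 so that each gives the same instruction.

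The cost is a short amendment and matching consent wording. Section 4.5 already asks these women to attend the 10-14 day visit, so no visit is added. The small downside is that a few women with malignancy stay in a benign-indication cohort; a sensitivity analysis excluding them addresses this.

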#### 5.0 STUDY INTERVENTION

## 5.1 Description

The study intervention is the performance of a backfill void trial versus an autofill void trial. These interventions are not experimental and have been described at length in the literature but not directly in our patient population.

